## **2.2. RESEARCH HYPOTHESIS**

The Research Question of the present trial is the following: in a population of adult patients, men and women, suffering from symptomatic haemorrhoids, will the administration for 4 weeks of the IMD PROCTOeze® PLUS improve the haemorrhoidal symptomatology, giving results assessed at the end of the treatment by means of validated questionnaires?

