	
from pain, burning, itching and other related complaints, contributing to the physiological restoration of the anal and perianal tissues. Its application leaves the treated area soft and moisturised, avoiding the onset of irritation and cracking of the skin. The lubricating action helps to facilitate bowel movement, thus minimising the trauma and pain sensation associated with defecation.
 
PROCTOEZE® PLUS key ingredients are mainly paraffinum liquidum, petrolatum, dimethicone, and hydroxyethylcellulose.
 
All the patients will use the MD PROCTOEZE® PLUS during the whole study according to Instruction for Use of the MD and to standard clinical practice.

Chronogram of visits	
The study envisages the following visits and phone follow up per patient:
 
 
• Visit 1, day 0: Screening / Baseline visit.
 
• Visit 2, day 14 (<math>\pm</math> 2 days):
 
• Phone follow up, day 30 (<math>\pm</math> 1 day).
 

Study duration	The study will last 30 days for each patient.

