Procedures	
Visit 1 Screening / Baseline visit (day 0)
 
 
• Informed consent / Eligibility Criteria
 
• Demographics / Medical History / Physical examination and vital signs (including haemorrhoids evaluation and confirmation of diagnosis)
 
• Concomitant treatments and medications assessment
 
• Quality of life assessment by means of the Short Health Scale for Haemorrhoidal Disease (SHSHD) by patient
 
• Haemorrhoid Severity Score (HSS) by Investigator
 
• Haemorrhoidal Disease Symptom Score (HDSS) by patient
 
• Diary supply
 
• MD supply
 
 
Visit 2 End of Study visit (day 14 <math>\pm</math> 2 days)
 
 
• Treatment adherence
 
• Diary's maintenance
 
• Physical examination and vital signs (including haemorrhoids evaluation)
 
• Concomitant treatments and medications assessment
 
• Quality of life assessment by means of the Short Health Scale for Haemorrhoidal Disease (SHSHD) by patient
 
• Haemorrhoid Severity Score (HSS) by Investigator
 
• Haemorrhoidal Disease Symptom Score (HDSS) by patient
 
• Diary collection
 
• MD collection
 
• Safety assessment by AE / ADE / DD collection
 
 
Phone call (day 30 <math>\pm</math> 1 day)
 
 
• Treatment adherence
 
• Diary's maintenance
 
• Safety assessment by AE / ADE / DD collection
 

Not allowed concomitant treatment or	Any drug or treatment mentioned in the eligibility criteria as not allowed will be forbidden during the study and its use will have to be avoided by patients, otherwise they are excluded from the participation: use of laser treatment,

medications	
steroidal or non-steroidal anti-inflammatory drugs, analgesics, any anti-haemorrhoidal treatment (both drugs and dietary supplements), anticoagulants, and antiplatelet agents will be not allowed during the whole study.
 
No restriction on treatments taken previously by patients for medical conditions not related to this study protocol will be envisaged.
 
Patients will be advised to note any concomitant treatment or medications or any major modification to their diet and / or lifestyle in the diary.

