### 3.7.2.1. Study visits

#### Visit 1 Screening / Baseline Visit (day 0)

At each Centre, patients will be enrolled consecutively. During this visit, patients who will meet the eligibility criteria (inclusion and exclusion criteria) will be enrolled after the signature of the informed consent form and will be informed verbally and in writing about the nature and requirements of the trial. Patients agreeing with the participation in the study will have to date and sign the informed consent form prior to any study-related procedure. All the screening procedures must be completed during this visit.

During this visit, the Investigator will collect information regarding medical history, demography, concomitant treatments and medications, AE/SAE if applicable. The Investigator will report data on the appropriate eCRF pages.

A physical examination will be performed, including evaluations of vital signs; pulse, blood pressure (diastolic and systolic), weight / height and BMI (kg/m^2) data will be collected. An evaluation of the haemorrhoidal disease will be performed, and a confirmation of the diagnosis and of the stage of haemorrhoids will take place, according to inclusion criteria (patients diagnosed with Grade I – II symptomatic haemorrhoids (according to Goligher classification, confirmed by clinical and anoscopic or proctoscopic examination performed within 3 months before baseline)

During this visit the following questionnaires will have to be completed:

- **HR-QoL questionnaire: SHSHD (by patient)**
- **HSS (by Investigator)**
- **HDSS (by patient)**

During this visit, the MD will be provided to each patient. The used, partially used and unused containers of the MD will have to be brought back to the centre on the last study visit. The MD will be supplied in the same package available on the market, and with the same leaflet / IFU – Instructions for Use.

A patient diary will be supplied; it will have to be completed at home by patients for the whole duration of the study. A series of information will have to be collected related to the health status of the patient (not an exhaustive list): use of any treatment or OTC or prescribed medications (concomitant treatments and medications), start and stop dates and name/dosage of the product will be collected; AE/ADE/DD occurrence; self-administration of the MD (according to IFU and standard clinical practice).

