The importance of duly completing the diary will be stressed by the Investigator. The completed diary will be collected at the end of the study (at V2). Patients will be advised to note any major modification to their diet

and / or lifestyle in the diary. Moreover, patients will be informed (it will be written in the diary) that they will receive a phone call from the investigator 30 days after the end of the study to check if there have been AEs. The following visit (V2) will be scheduled 14 ( $\pm$  2) days after V1; a phone call will be scheduled 30( $\pm$  1) days after V1.

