#### Visit 2 (day 14 $\pm$ 2 days)

During this visit, the Investigator will perform the following examinations and the e-CRF will be completed accordingly:

- Physical examination (according to what was already performed at visit 1: pulse, blood pressure, weight / height and BMI will be evaluated), including haemorrhoidal disease evaluation.
- Concomitant treatments and medications assessment.
- Evaluation of compliance (MD administration assessment by means of the patient's diary carried out by Investigator).
- Diary and MD (used, partially used, or unused containers) collection.
- Safety assessment by AE/ADE/DD collection.

During this visit the following questionnaires will have to be completed:

- HR-QoL questionnaire: SHSHD (by patient)
- HSS (by Investigator)
- HDSS (by patient)

Patients who discontinued the protocol, will be visited reporting on the last visit page all the safety assessments and (if possible) the examinations and questionnaires requested for the last visit.

Patients who discontinued the protocol, will be visited reporting on the last visit page all the safety assessments and (if possible) the questionnaires requested for the last visit.

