## 5. PATIENT DIARY

Visit data   .   .

Compilation instruction

Please from tomorrow for 14 days each day fill this diary.

In the first column insert the data, in the column from two to six put a cross at any Proctinus cream application.

If you take any drug note in the other drug column the name of each drug taken

In the general health column insert information if you have any different disease than hemoroides.

In the column note insert any other relevant information.

For any doubt on the diary filling please contact the doctor of this study

Dr. \_\_\_\_\_ contact number \_\_\_\_\_

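### The protocol asks a 4-week treatment question, but its procedures collect the device and a 14-day diary at day 14 ± 2, and nothing reconciles the two durations

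*Combined protocol and SAP*

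**What the plan says.** **Four weeks or day 30.** Protocol section 2.2 asks "will the administration for 4 weeks of the IMD PROCTOeze® PLUS improve the haemorrhoidal symptomatology"; the Summary and the Synopsis pose the same question. Section 3.5.1 places all three scales at day 30, and the Synopsis does the same and equates day 30 with the end of treatment. Section 4.3.1 assumes an effect after 4 weeks of treatment. The Synopsis has patients using the device throughout the study and adds "The study will last 30 days for each patient". It lists adherence and diary checks at the day-30 call, and both schedules of assessments list compliance there. Section 3.4.1 also relies on a diary kept for the whole study.

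**About 14 days.** The schedules show device and diary supplied at Visit 1 only. Under Visit 1, section 3.7.2.1 says "The used, partially used and unused containers of the MD will have to be brought back to the centre on the last study visit". Under Visit 2, at day 14 ± 2, it lists "Diary and MD (used, partially used, or unused containers) collection". The Synopsis heads that visit "Visit 2 End of Study visit (day 14", and section 3.7.2.1 says "The completed diary will be collected at the end of the study (at V2". The diary form instructs "Please from tomorrow for 14 days each day fill this diary". In section 3.7.2.1 the day-30 contact is a telephone call for safety only.

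**The analysis.** Report section 9 describes 14 days of diary data and treats Visit 2 as the end of treatment. The Summary mentions a 14-day monitoring period for the diary, but its discussion and conclusions state no duration.

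**The concern.** Duration is part of what the intervention is. A trial that asks about 4 weeks, and whose procedures end device use at about 2, answers a different question from the one posed. The Summary puts an undated claim of performance and safety beside a 4-week question, so the claim can be taken as its answer. The absence of adverse events has the same limit: it rests on about 14 days of documented use plus follow-up to day 30. The results are intended for the Notified Body as post-market evidence, so the length of use they cover should be explicit.

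**Working it through.** **1. Sample size, and what it is tied to.** Section 4.3.1 gives 7.90 (SD 4.17) before treatment and assumes 6.20 (SD 0.25) after 4 weeks. The paired effect size is dz = (7.90 − 6.20) / √(4.17² + 0.25² − 2r × 4.17 × 0.25). The protocol gives no correlation r. With r = 0.5 assumed, dz = 1.70 / 4.051 = 0.420, matching the stated value of about 0.42 (0.407 at r = 0, 0.434 at r = 1). For a one-sided 2.5% Wilcoxon signed-rank test with 80% power, using the noncentral t with n scaled by 3/π (normal parent), n = 49 against 50 stated; power at 50 is 81.1%. The arithmetic is sound. The effect it uses is labelled as a 4-week effect.

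**2. Timing of collection.** The Visit 2 window is day 14 ± 2, that is day 12–16.
- Share of 30 days: 12/30 = 40% to 16/30 = 53%.
- Share of 28 days: 12/28 = 43% to 16/28 = 57%.
- Gap to the call at day 29–31: 29 − 16 = 13 to 31 − 12 = 19 days.

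These figures use the protocol window alone. A narrower range of day 14–16 would follow if diary day 1 was the day after Visit 1, as the form instructs. Table 4.1 makes that uncertain: 42% of patients recorded a single application on day 1, against 2–10% on the other days, which is what a partial first day would produce.

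**3. Documented exposure.**
- Table 4.1, day 14: 5 + 30 + 14 + 1 = 50, so all patients have an entry.
- Patient-days recorded: 50 × 14 = 700. Two entries are zero (one on day 3, one on day 5), leaving 698 with at least one application.
- Stated course: 50 × 28 = 1,400 or 50 × 30 = 1,500 patient-days.
- The 14 daily means in Table 4 sum to 34.44, the reported total, so the reported usage covers those 14 days only.

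**4. End-of-treatment dates.** The Summary's timing table puts end of treatment on 16 January 2025, which is 30 days after the last patient in (17 December 2024). For that patient, Visit 2 was due on 31 December (29 December to 2 January), yet report section 9 calls Visit 2 the end of treatment.

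**5. Attempted reconciliation.** The diary conflict has a partial way out. Section 3.7.2.1 says of the diary "it will have to be completed at home by patients for the whole duration of the study", and if the study ends at Visit 2, as that section also says, this means 14 days. That reading contradicts the 30-day study duration in the Synopsis. No text reconciles the day-30 end of treatment with collection at day 14.

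**The case against.** The strongest reply is that the documents are less obscure than this suggests. The Summary mentions 14 days of diary monitoring, section 9 speaks of 14 days and compares Visit 1 with Visit 2, and the schedules put Visit 2 at day 14. A careful reader can infer that the results concern about 14 days. That stands, so it would be too strong to say the duration cannot be worked out. What is missing is a statement of it in the conclusions, or any acknowledgement that it differs from the question.

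Some stronger readings are tempting but unsupported:
- **That patients received only a 14-day supply.** The quantity dispensed is not stated; what is documented is single dispensing and collection at Visit 2.
- **That every device did come back at day 14.** The case report form has device-collection boxes on both the Visit 2 page and the call page. The call page also lists a physical examination and looks copied, so it is weak evidence either way. The end-of-treatment date in the timing table is also weak, because it fits the last safety call equally well.
- **That the trial was underpowered.** No 14-day effect is given. Purely as illustration, if 100%, 75% or 50% of the assumed effect size were present at day 14, n would be 49, 85 or 189, and power at 50 would be 81%, 57% or 30%. The assumed change of 1.70 was in any case the authors' own reduction from the 3.85 (7.90 − 4.05) in the cited study, and the completed trial reports P < 0.0001.

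The inclusion criterion mentioning 30 days asks only for ability to self-administer, so it is not counted as evidence of a 30-day course.

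**Conclusion.** The point holds: current protocol text states two treatment durations, and the schedule followed as written does not test the 4-week question. Device collection falls at 40–53% of 30 days or 43–57% of 28, which is 13–19 days before the day-30 call. Recorded use is 700 patient-days out of 1,400–1,500. N = 50 and the P values do not change; what changes is the course to which the results apply. The percentages assume that visits kept their windows. That use actually stopped at Visit 2 is the natural reading of the procedures, but completed records must confirm it: a 14-day diary cannot show whether use continued.

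**What to change.** 1. Confirm from completed case report forms and site records the contact at which each device was returned. List each patient's Visit 1 to Visit 2 interval from the dates in sections 4 and 6 of the form.
2. If return was at Visit 2, state one duration in the study report: about 14 days of treatment, with a safety call at day 30. Identify as superseded:
   - the 4-week, day-30 end-of-treatment and whole-study-use wording in the Summary (including its timing table), the Synopsis, and protocol sections 2.2, 3.4.1 and 3.5.1 (including the primary outcome);
   - the day-30 adherence, diary and compliance items in the Synopsis and schedules;
   - the call placed 30 days after the end of the study in sections 3.6.2 and 3.7.2.1.
3. Keep the sample-size figures, and note that the assumed effect refers to 4 weeks.
4. Limit the performance conclusion to about 14 days of use, or to the actual interval if visits were late. Limit the safety conclusion to about 14 days of documented use with follow-up to day 30. Say that the 4-week question was not tested.
5. If some patients kept the device after Visit 2, report that later use was not recorded and that their scales were scored before the end of treatment.

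Handle this together with any point on day-14 versus day-30 scoring of the endpoints, which has the same root. The cost is a records check, one listing and a report clarification, with no new patients or procedures. The downside is that the conclusions no longer cover a 4-week course.

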## **2.3. STUDY OBJECTIVES**

This trial aims to evaluate the overall performance and safety of the MD PROCTOeze® PLUS in relieving symptomatology of haemorrhoidal disease and anal irritation in adult patients affected by Grade I-II (Goligher classification) haemorrhoids as assessed by the patient and the Investigator at the end of the treatment period.

The primary objective is the assessment of performance by the improvement in the quality of life (QoL). Secondary objectives are the assessment of performance by validated scales completed by the Investigator and by the patient at the end of the treatment period.

The safety of the MD will be evaluated through AE and ADE incidence assessed by Investigators and reported according to the current legislation.

## **JUSTIFICATION FOR THE TRIAL**

The protocol is based on what is already known on both the topic object of the study, i.e., the symptomatic treatment of haemorrhoids, and the investigational medical device, according to which is shortly summarized in section 2.1. MD PROCTOeze® PLUS is a specific adjuvant for the symptomatic relief of internal and external haemorrhoids and anal irritation. Due to its formulation, it contributes to the physiological restoration of the anal and perianal tissues.

The tool used in this research is a PMCF, a procedure which, through a scientific method of detection (one or more questionnaires to be submitted to a representative sample of patients related to the issue of the research), allows to collect, and subsequently analyse, the data needed to study the relationships between different variables.

## **3. PROCEDURES**

---

### **3.1. DESIGN**

Open, non-comparative, multicentre, prospective, interventional trial.

### **3.2. STUDY SETTING**

Sites located in Romania (i.e., the clinical centres), will be involved

### **3.3. SELECTION OF POPULATION**

The study population will include 50 evaluable patients, afferent at the study Centres. These patients will be asked for informed consent and verified for the inclusion and exclusion criteria.

### 3.3.1. Inclusion criteria

Patients will be eligible for inclusion if **ALL** the following criteria are respected:

- Men and women  $\geq$  18 years old.
- Patients diagnosed with Grade I – II symptomatic haemorrhoids (according to Goligher classification) confirmed by clinical and anoscopic or proctoscopic examination performed within 3 months before baseline.
- Patients able to do self-administration at home of the MD, for 30 days, to treat symptoms of haemorrhoids and anal irritation.
- Patient free from the following treatments for haemorrhoids for at least 4 weeks: laser treatments for haemorrhoids, steroid or non-steroidal anti-inflammatory drugs, analgesics, any anti-haemorrhoidal treatment, anticoagulants, and antiplatelet agents.
- Patients able to communicate adequately with the Investigator and understand the questionnaire.
- Patients able to understand and who can provide valid informed consent to the trial.

### 3.3.2. Exclusion criteria

Patients fulfilling one or more of the following exclusion criteria will **NOT** be included in the study:

- Inflammatory and infectious disease of the digestive tract (e.g., IBD – Inflammatory Bowel Disease).
- Frequent hemorrhoidal bleeding
- Severe, uncontrolled hypertension, renal failure, cirrhosis, colorectal cancer, anal fissure or fistula.
- Patients with known sensitivity to the tested medical device or its components.
- Patients with any other medical condition that, in the opinion of the Investigator, would compromise participation or be likely to lead to hospitalisation during the study.
- Participation in an interventional clinical study or administration of any investigational agents in the previous 30 days. Patients considered smokers ( $\geq 10$  cigarettes/day).
- Energy-restricted diet for weight loss.
- Pregnant woman, lactating woman, and woman of childbearing potential who is planning a pregnancy or is unwilling to use appropriate methods of contraception\* during the study.  
\*Methods of contraception: hormonal contraceptive, intrauterine device or intrauterine system, double barrier method (condom with spermicide/diaphragm or cervical cap with spermicide), surgical sterilization (vasectomy, tubal ligation, etc.).
- Patients unlikely to cooperate.
- Patients with any other medical condition that, in the opinion of the Investigator, would compromise participation or be likely to lead to hospitalisation during the study.
- Participation in an interventional clinical study or administration of any investigational agents in the previous 30 days.

### 3.3.3. Patient identification

Each patient enrolled will be identified by the patient number, a five digits code (e.g., 01.001), which will be the only identification element and will be used only for the purposes of this study. This code will consist of the Centre number (e.g., 01/02/etc. corresponding to each Centre) and of the sequence number of the patient (e.g., .001, which means the 1st patient enrolled). If the patient is declared a screening failure (one or more eligibility criteria is not fulfilled and the patient cannot participate in the study), the identification code will not be reassigned to another patient.

### **3.3.4. Patient Enrolment and allocation**

Once the eligibility is established according to inclusion/exclusion criteria, ICF signed, patients will be enrolled

### **3.3.5. Number of patients**

Fifty fully evaluable patients will be included in the study.

### **3.3.6. Withdrawal or discontinuation criteria and procedures; patient lost to follow up**

Patients may withdraw at any time at their own request. The centre must inform the CRO personnel when a patient withdraws from the study.

The Investigator will complete and sign the appropriate CRF when a patient is lost to follow-up. The date and type of attempted communication with the patient will also be documented.

## **3.4. MEDICAL DEVICE DESCRIPTION**

PROCTOeze® PLUS is a soft and light hydrophilic emulsion that provides protection to irritated areas. It is a specific adjuvant for the symptomatic relief of internal and external haemorrhoids and anal irritation. The product creates a physical barrier that protects the peri-anal tissue, minimizing the possibility of bacterial colonization and contact with local and environmental agents, which may exacerbate haemorrhoid conditions. Due to its formulation, it contributes to the physiological restoration of the anal and perianal tissues. PROCTOeze® PLUS has a protective, lubricating and refreshing action. PROCTOeze® PLUS has emollient properties, which help to prevent irritation and discomfort of the perianal area, providing relief from pain, burning, itching and other related complaints. Its application leaves the treated area soft and moisturised, avoiding the onset of irritation and cracking of the skin. The lubricating action helps to facilitate bowel movement, thus minimising the trauma and pain sensation associated with defecation. It also supports the physiological repairing process.

Key ingredients of IMD paraffinum liquidum, petrolatum, dimethicone and hydroxyethylcellulose (Annex 1 "Product composition"), appropriately provided with study-specific labels.

The MD will be supplied in the same package available on the market, and with the same leaflet / IFU – Instructions for Use.

